5.2 Variables Used for Stratification of Randomization

Approximately 1650 subjects will be enrolled to receive ABT-450/r/ABT-267 and ABT-333 with or without RBV depending on their HCV genotype and cirrhotic status. No stratification of randomization will be used for this study.

6.0 Analysis Conventions

ICON Inc is the central laboratory used in this study. The chemistry platform will be transitioned from the Roche Diagnostics Hitachi Modular System (old) to the Abbott Architecture (new) in January 2016 while the study is expected to be still on-going. The

chemistry data obtained from the old chemistry platform will be converted to the new chemistry platform and the converted data will be combined with the data obtained from the new system for all statistical analysis and the normal ranges associated with the new chemistry platform will be applied. The analysis of mean changes from baseline, shifts above and below the normal ranges, the flagging of potentially clinically significant (PCS) laboratory data, and the CTCAE grading of chemistry labs will be performed as if all the chemistry data were generated by one platform – the new chemistry platform.

6.1 Baseline and Final Value

6.1.1 Baseline

The baseline value refers to the last non-missing measurement collected before the first dose of study drug. All assessments on Study Day 1 should be performed prior to administering the first dose of study drug, in accordance with the protocol. The baseline value is therefore determined by the last non-missing measurement collected on or before the first day of study drug administration.

If multiple measurements are recorded on the same day, the last measurement recorded prior to dosing will be used as the baseline value. If these multiple measurements occur at the same time or time is not available, then the average of these measurements (for continuous data) or the worst among these measurements (for categorical data) will be considered as the baseline value. This same baseline value will be used for Treatment and PT Periods.

Safety assessments that are related to a serious adverse event that occurs on the first dose day are excluded when applying this algorithm.

6.1.2 Study Days

Study days (days relative to the first dose of study drug) are calculated for each time point relative to the first dose of study drug. Study Days are negative values when the time point of interest is prior to the first study drug dose day. Study Days are positive values

when the time point of interest is after the first study drug dose day. There is no Study Day 0. Study Day 1 is the day of the first dose of study drug.

6.1.3 Study Drug End Days

For all subjects who receive at least one dose of study drug, study drug end days (days relative to the last dose of study drug) are calculated relative to the last dose of study drug. The last day of study drug is defined as Study Drug End Day 0. Days before it have negative study drug end days and days after it have positive study drug end days.

6.1.4 Final Treatment Value

The final treatment value for each subject is the last non-missing measurement collected after Study Day 1 and on or before Study Drug End Day 2.

6.1.5 Final Post-Treatment Value

The final post-treatment value for each subject is the last non-missing measurement collected after Study Drug End Day 2.

6.2 Analysis Windows

For efficacy analyses of HCV RNA and resistance, the time windows specified in [Table 2](#) and [Table 3](#) describe how efficacy data are assigned to protocol-specified time points during the Treatment and PT Periods, respectively. All time points and corresponding time windows are defined based on the blood sample collection date.

For analyses of health-related quality of life (QoL) PROs collected throughout the study, the time windows specified in [Table 4](#) will be used.

For laboratory data and vital signs, the time windows specified in [Table 5](#) and [Table 6](#) describe how data are assigned to protocol specified time points during the Treatment and PT Periods, respectively.

If more than one assessment is included in a time window, the assessment closest to the nominal time will be used. If there are two observations equally distant to the nominal time, the latest one will be used in analyses. The only exception to this is for the SVR windows (e.g., SVR₄, SVR₁₂, and SVR₂₄); for these windows, the last value in the window will be used.

If multiple measurements are made on the same day for a safety laboratory parameter or a vital sign parameter, the average of the values will be used in analyses. For summaries of shifts from baseline and potentially significant values, multiple values on the same day will not be averaged; all values will be considered for these analyses.

Table 2. Analysis Time Windows for HCV RNA and Resistance Endpoints (Treatment Period)

Scheduled Visit	Nominal Day (Study Day)	Time Window (Study Day Range)
Day 1/Baseline ^a	1a	≤ 1 ^a
Week 2	14	2 to 21
Week 4	28	22 to 56
Week 12	84	57 to 126
Week 24 ^b	168	127 to 182
Final Treatment Visit ^c		2 to ≤ 2 days after last dose of study drug

a. Day of first dose of study drug.

b. Week 24 Visit is only applicable to subjects assigned to 24 weeks of treatment.

c. The last value within the window will be used to define the Final Treatment visit value.

Note: Data must also have Study Drug End Day ≤ 2 for all windows. The result closest to the scheduled time point will be used.

Table 3. Analysis Time Windows for HCV RNA and Resistance Endpoints (Post-Treatment Period)

Scheduled Visit^a	Nominal Day (Study Drug End Day)	Time Window (Study Drug End Day Range)
Post-Treatment Week 4	28	3 to 56
Post-Treatment Week 12	84	57 to 126
Post-Treatment Week 24	168	127 to 266
Post-Treatment Week 52	364	267 to 546
Post-Treatment Week 104	728	547 to 910
Post-Treatment Week 156	1092	911 to 1274
Post-Treatment Week 208	1456	1275 to 1638
Post-Treatment Week 260	1820	1639 to 2002
SVR ₄ ^b	28	3 to 56
SVR ₁₂ ^b	84	57 to 126
SVR ₂₄ ^b	168	127 to 210

a. Post-Treatment Visits are applicable for subjects who received at least one dose of study drug.

b. For SVR windows, the last value in the window will be used.

Note: The result closest to the scheduled time point will be used, except for SVR₄, SVR₁₂, and SVR₂₄. Data must also have Study Drug End Day > 2 for all windows. Study Drug End Day 0 is defined as the day of the last dose of study drug.

Table 4. Analysis Time Windows for PRO Instruments

Scheduled Visit^a	Nominal Day (Study Day)	Time Window (Study Days Range)
Day 1/Baseline	1 ^b	≤ 1 ^b
Week 4	28	2 to 56
Week 12	84	57 to 126
Week 24 ^c	168	127 to 182
Final Treatment Visit ^d		2 to ≤ 2 days after last dose of study drug

Scheduled Visit	Nominal Day (Study Drug End Day)	Time Window (Study Drug End Days Range)
Post-Treatment Week 4	28	3 to 56
Post-Treatment Week 12	84	57 to 126
Post-Treatment Week 24	168	127 to 266
Post-Treatment Week 52	364	267 to 546
Post-Treatment Week 104	728	547 to 910
Post-Treatment Week 156	1092	911 to 1274
Post-Treatment Week 208	1456	1275 to 1638
Post-Treatment Week 260	1820	1639 to 2002
Final Post-Treatment Visit ^e		> 2 days after last dose of study drug

a. SF-36v2 and FACIT-F are collected at Baseline, Week 4, Week 12 and Week 24 (for subjects with 24 weeks of treatment), and Post-Treatment Weeks 4, 12, 24, 52, 104, 156, 208 and 260.

b. Day of first dose of study drug.

c. Applicable to subjects with 24 weeks of treatment.

d. The last value within the window will be used to define the Final Treatment visit value. The upper bound of this Final window is Study Drug End Day ≤ 2.

e. The last value within the Post-Treatment Period window will be used to define the Final Post-Treatment visit value. The lower bound of this Final window is Study Drug End Day 3.

Note: The result closest to the scheduled time point will be used. For visits through Treatment Week 24, data must also be within 2 days after the last dose of study drug. For post-treatment visits, data must also have Study Drug End Day > 2 where Study Drug End Day 0 is defined as the day of the last dose of study drug.

Table 5. Laboratory Data and Vital Sign Visit Windows (Treatment Period)

Scheduled Time	Nominal Day (Study Day)	Time Window (Study Days Range)
Day 1/Baseline ^a	1	≤ 1
Week 2	14	2 to 21
Week 4	28	22 to 56
Week 12	84	57 to 126
Week 24 ^b	168	127 to 182
Final Treatment Visit ^c		2 to ≤ 2 days after last dose of study drug

a. Day of first dose of study drug.

b. Applicable to subjects with 24 weeks of treatment.

c. The last value within the window will be used to define the final on-treatment value. The upper bound of this Final window is Study Drug End Day ≤ 2.

Note: The result closest to the scheduled time point will be used. Data must also be ≤ 2 days of the last dose of study drug. Total Insulin is measured at baseline, Week 12, Week 24 (for subjects on 24-week treatment regimen only), or EOT, and will use those visit windows as defined above.

Table 6. Laboratory Data and Vital Sign Visit Windows (Post-Treatment Period)

Scheduled Time	Nominal Day (Study Drug End Day)	Time Window (Study Drug End Days Range)
Post-Treatment Week 4	28	3 to 56
Post-Treatment Week 12	84	57 to 126
Post-Treatment Week 24	168	127 to 266
Post-Treatment Week 52	364	267 to 546
Post-Treatment Week 104	728	547 to 910
Post-Treatment Week 156	1092	911 to 1274
Post-Treatment Week 208	1456	1275 to 1638
Post-Treatment Week 260	1820	1639 to 2002
Final Post-Treatment Visit ^a		> 2 days after last dose of study drug

a. The last value within the Post-Treatment Period window will be used to define the final post-treatment value.

Note: The result closest to the scheduled time point will be used. Data must also have Study Drug End Day > 2. Vital signs and hematology, chemistry, urinalysis, and coagulation panels are collected at every Post-Treatment Period visit. Urinalysis is not conducted after PT Week 4. Total Insulin is collected at Post-Treatment Weeks 52, 104, 156, 208, and 260 and will use those visit windows as defined above. FibroTest samples are collected at Post-Treatment Weeks 12 (or upon study discontinuation) and will use those visit windows as defined above.

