11.3 Analysis of Laboratory Data

Data collected from central and local laboratories, including additional lab testing due to all SAE will be used in all analysis.

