11.3.2 Statistical Methods

Clinical laboratory tests will be summarized at each visit during the Treatment Period. The baseline value will be the last measurement on or before the day of the first dose of study drug. This same baseline value will be used for all change from baseline tables in the Treatment Period and Post-Treatment Periods.

Mean changes from baseline to each post-baseline visit, including applicable post treatment visits, will be summarized for each protocol-specified laboratory parameter with the baseline mean, visit mean, change from baseline mean, standard deviation, and median.

Laboratory data values will be categorized as low, normal, or high based on normal ranges of the laboratory used in this study. Shift tables from baseline to minimum value, maximum value, and final values during the Treatment Period (Study Drug End Day \leq 2) will be created. The shift tables will cross tabulate the frequency of subjects with baseline values below/within/above the normal range versus minimum/maximum/final values below/within/above the normal range.

The number and percentage of subjects with post-baseline values during the Treatment Periods meeting the specified criteria for Potentially Clinically Significant (PCS) laboratory values (defined in [Table 8](#) and [Table 9](#)) will be summarized. A post-baseline value must be more extreme than the baseline value to be considered a PCS finding. A separate listing will be provided that presents all lab values for the subjects meeting PCS criteria during treatment.

For hemoglobin and the liver function tests (LFTs) of alkaline phosphatase and total bilirubin, the number and percentage of subjects with a maximum Common Terminology Criteria for Adverse Events (CTCAE) Grade of 1, 2, 3, or 4 (see definitions in [Table 10](#)) at any post-baseline visit (regardless of the baseline value) through the end of treatment (i.e., Final Treatment Value) will be summarized. All LFT tables will include summary rows for the number and percentage of subjects with at least Grade 2 and at least Grade 3 laboratory abnormalities. The hemoglobin table will include a summary row for the number and percentage of subjects with at least a Grade 2 laboratory abnormality.

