For the liver function tests (LFTs) of ALT and AST, the number and percentage of subjects with a maximum Common Terminology Criteria for Adverse Events (CTCAE) Grade of 1, 2, 3, or 4 (see definitions in [Table 10](#)) at any post-nadir visit (regardless of the baseline value) through the end of treatment (i.e., Final Treatment Value) will be summarized. Note, for these analyses, the nadir is used for reference instead of baseline. Both ALT and AST tables will include summary rows for the number and percentage of subjects with at least Grade 2 and at least Grade 3 laboratory abnormalities.

Accompanying listing of hemoglobin results will be provided for any subjects with at least Grade 2 hemoglobin abnormalities. Accompanying listings of all ALT, AST, total, indirect and direct bilirubin, and alkaline phosphatase will be created for any subject who had at least a Grade 3 ALT, AST, alkaline phosphatase, or total bilirubin. A listing of the hematology results will be provided for subjects with hemoglobin abnormalities.

Table 10. Definitions of CTCAE Grades 1, 2, 3, and 4

Test	Grade 1	Grade 2	Grade 3	Grade 4
ALT/SGPT	> ULN – 3 × ULN	> 3 – 5 × ULN	> 5 – 20 × ULN	> 20 × ULN
AST/SGOT	> ULN – 3 × ULN	> 3 – 5 × ULN	> 5 – 20 × ULN	> 20 × ULN
Alkaline Phosphatase	> ULN – 2.5 × ULN	> 2.5 – 5 × ULN	> 5 – 20 × ULN	> 20 × ULN
Total Bilirubin	> ULN – 1.5 × ULN	> 1.5 – 3 × ULN	> 3 – 10 × ULN	> 10 × ULN
Hemoglobin Decreased	< LLN – 100 g/L	< 100 – 80 g/L	< 80 – 65 g/L	< 65 g/L

The number and percentage of subjects meeting the following criteria will be summarized:

- ALT $\geq 3 \times$ ULN and total bilirubin value $\geq 2 \times$ ULN;
- ALT $> 5 \times$ ULN (equivalent to Grade 3 or higher) and total bilirubin value $< 2 \times$ ULN.

A subject or event will be counted if the post-nadir laboratory values meet the above criteria regardless of the baseline laboratory value (i.e., the post nadir laboratory value does not need to be worse than the baseline laboratory value). The maximum ratio relative to the ULN will be used to determine if subjects meet the criteria listed above.

For subjects meeting the ALT $\geq 3 \times$ ULN and total bilirubin value $\geq 2 \times$ ULN criterion during the Treatment Period, a corresponding listing of all ALT, AST, alkaline phosphatase, and total, direct, and indirect bilirubin values will be provided.

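### SAP 6.2 averages same-day laboratory values without exempting the maximum CTCAE grade tables or the ALT/bilirubin criteria, so a literal reading can understate a maximum grade

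*SAP*

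**What the plan says.** SAP 6.2 reduces repeated measurements by two rules.

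- Windows: "If more than one assessment is included in a time window, the assessment closest to the nominal time will be used". Ties go to the later value, and the only stated exception is for the SVR windows.
- Same day: "If multiple measurements are made on the same day for a safety laboratory parameter or a vital sign parameter, the average of the values" is what the analyses use. The exemption follows: "For summaries of shifts from baseline and potentially significant values, multiple values on the same day will not be averaged", and every value counts there.

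SAP 6.0, on the change of chemistry platform, names as separate items "the flagging of potentially clinically significant (PCS) laboratory data, and the CTCAE grading of chemistry labs".

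SAP 11.3 says of sources: "Data collected from central and local laboratories, including additional lab testing due to all SAE will be used in all analysis".

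SAP 11.3.2 tabulates the maximum CTCAE grade for hemoglobin, alkaline phosphatase and total bilirubin "at any post-baseline visit (regardless of the baseline value) through the end of treatment". ALT and AST are graded over post-nadir visits: "Note, for these analyses, the nadir is used for reference instead of baseline". Two combined criteria follow: ALT at least 3 x ULN with bilirubin at least 2 x ULN, and ALT above 5 x ULN with bilirubin below 2 x ULN. For these, "A subject or event will be counted if the post-nadir laboratory values meet the above criteria regardless of the baseline laboratory value", judged on the largest multiple of ULN. The nadir is not defined.

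**The concern.** A maximum-grade table is meant to show each subject's worst value. Averaging two values from one day replaces the worse one with something milder. The SAP recognises this for shift and potentially significant value summaries and switches averaging off there, but it does not do so for the grade tables or the ALT/bilirubin criteria, where the same reasoning applies. Because SAP 6.0 treats PCS flagging and CTCAE grading as different analyses, the exemption does not naturally stretch to cover grading.

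What is at stake is the count of Grade 3 or higher abnormalities in the safety report. Bilirubin is the row most likely to be read: Protocol Table 3 gives Grade 3 rates of 2.6% to 13.5% in the Phase 3 ribavirin arms. The primary analysis is not affected.

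**Working it through.** The plan gives no figure to reproduce. The check applies the SAP 6.2 rules to the grade limits in SAP Table 10. The laboratory values are illustrative.

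**1. Same-day averaging.** Assume both values share one ULN; the SAP gives no rule for differing ULNs.

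- Total bilirubin 2.8 and 3.1 x ULN: (2.8 + 3.1)/2 = 2.95. Grade 3 starts above 3 x ULN, so the subject is Grade 2 instead of Grade 3.
- Hemoglobin 8.4 and 7.8 g/dL: (8.4 + 7.8)/2 = 8.1 g/dL, or 81 g/L. Grade 3 starts below 80 g/L, so again Grade 2 instead of Grade 3.

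A mean cannot exceed the largest of its values or fall below the smallest. For hemoglobin, alkaline phosphatase and total bilirubin the reported maximum grade is therefore right or too low. In the combined criteria, an averaged bilirubin that slips below 2 x ULN could move a subject from the first criterion to the second.

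**2. Window selection, if it applies to these tables.** In SAP Table 5 the Week 2 window is Days 2 to 21 with nominal Day 14. Bilirubin of 3.4 x ULN on Day 8 is 6 days from nominal; 2.6 on Day 14 is 0 days away. Day 14 is kept, and Grade 3 becomes Grade 2. This result is conditional; see the objection.

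**3. The nadir.** Take ALT on Days 1/14/28/31/38/50/84 = 4.0/1.3/6.0/6.4/3.0/1.2/1.4 x ULN, using all values.

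- Nadir as the overall lowest value: 1.2 on Day 50. The only later value is 1.4, so Grade 1. The rise to 6.4 disappears.
- A value counted when it exceeds the lowest value on any earlier day: 6.4 exceeds 1.3 and counts, so Grade 3.

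Using all values without defining the nadir can therefore hide a real elevation. Under the second definition, averaging or selection can only leave the ALT or AST grade equal or lower it. A value that exceeds the lowest of the earlier reduced values also exceeds the lowest of all earlier values, and the unreduced value that day is at least as large.

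**4. Cover from the PCS summaries.** These consider all same-day values.

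| Test | PCS limit (SAP Tables 8 and 9) | Grade 3 starts (SAP Table 10) | Grade 3 visible in PCS table? |
|---|---|---|---|
| Hemoglobin | < 8.0 g/dL | < 80 g/L | Yes, same limit |
| ALT, AST | > 5 x ULN and >= 2 x baseline | > 5 x ULN | Yes if baseline <= 2.5 x ULN, since 2 x 2.5 = 5 |
| Total bilirubin | >= 2.0 x ULN | > 3 x ULN | No; only in the PCS listing |
| Alkaline phosphatase | > 1.5 x ULN | > 5 x ULN | No; only in the PCS listing |

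With an ALT baseline of 4.0 x ULN, the PCS rule needs 2 x 4.0 = 8.0 x ULN, so a value of 5.8 is Grade 3 but not PCS.

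**The case against.** The strongest reply is that SAP 11.3 already means all values. It brings local and SAE-related tests into every analysis, grades at any post-baseline visit, and uses the largest ratio to ULN. The protocol calls extra attendances unscheduled visits, so a Day 8 sample is arguably such a visit. SAP 6.2 itself introduces the laboratory windows as a way to assign data to scheduled time points, and a maximum-grade table is not organised by time point. On window selection this largely stands. A reader might infer that SAP 6.2 discards unscheduled peaks from the grade tables, but the documents do not establish that; they leave it unclear. The reply does not reach same-day averaging. A sentence about data sources does not say how two values from one day are combined, and if it did, the shift and PCS exemption would be unnecessary.

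A reader might also infer that SAP 6.2 makes ALT and AST grades err in both directions. Overstatement relative to all values arises only if the nadir is taken as the overall lowest value, which the SAP does not say. In the series above, the windowed Grade 3 would in fact be the clinically right answer. The fault there is the missing definition.

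Two further points stand. Protocol 6.7.2 does not require confirmation of Grade 3 bilirubin, so repeat bilirubin values are not routinely generated. They come mainly from the ALT work-up in Protocol 6.7.5, from repeats of clinically significant results, or from local testing. And SAP 6.2 exempts potentially significant values without using the defined PCS term; reading the two as the same is an inference, though SAP 6.0 supports it.

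**Conclusion.** The point holds as a minor one, for same-day averaging. As written, SAP 6.2 applies averaging to analyses that report a worst value, and for hemoglobin, alkaline phosphatase and total bilirubin the error can only be towards a milder grade. This rests on a literal reading of the exemption and on subjects having more than one value on a day. Neither the number of such days nor the resulting change in any table can be computed from the documents. The bilirubin rates from Phase 3 show that the row matters, not that it would be wrong by any given amount.

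The window question is an ambiguity to close, not a demonstrated error. The undefined nadir needs settling at the same time, because moving to all values makes its definition matter more. PCS tables and listings limit the practical harm: hemoglobin is covered, ALT and AST are covered for baselines up to 2.5 x ULN, and Grade 3 bilirubin and alkaline phosphatase remain visible only in the listing.

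**What to change.** In SAP 6.2, extend the existing exemption: the maximum CTCAE grade tables and the ALT/bilirubin criteria use all on-treatment values (Study Drug End Day <= 2), scheduled and unscheduled, central and local, with neither same-day averaging nor window selection. Keep both rules for by-visit mean changes.

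In SAP 11.3.2, state that an ALT or AST value counts as post-nadir when it exceeds the lowest value on any earlier day, from baseline on. A later low re-test then cannot erase an earlier elevation. This is close to the trigger in Protocol 6.7.5, which looks for a rise over the previous measurement.

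The cost is two sentences and some programming, with no new data. Reported grades may look slightly less favourable. Small rebounds during the early fall in ALT would also count: in the sequence 8.0, 6.0, 6.1, 2.0, 1.0 x ULN, the 6.1 exceeds 6.0 and is reported as Grade 3.

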6.3 Missing Data Imputation

No data will be imputed for any efficacy or safety analyses except for the PRO questionnaires, for analyses of the HCV RNA endpoints, and for analysis of the persistence of resistance. If a respondent answers at least 50% of the items in a multi-item scale of the SF-36v2, the missing items will be imputed with the average score of the answered items in the same scale. In cases where the respondent did not answer at least 50% of the items, the score for that domain will be considered missing. Similarly, the missing items of the FACIT-F questionnaire will be imputed with the average score of the answered items in the same scale as long as more than 50% (≥ 7 out of 13) of the items in the scale are answered. The SF-36v2 Mental and Physical Component Summary measures will not be computed if any domain is missing.

HCV RNA values will be selected for an SVR analysis based on visit windows as defined in Section 6.2. When there is no HCV RNA value in a visit window based on defined visit windows, the closest values before and after the window, regardless of the value chosen for the subsequent and preceding window, will be used for the flanking imputation described below.

If a subject has a missing HCV RNA value at a post-Day 1 visit but with undetectable or unquantifiable HCV RNA levels at both the preceding value and succeeding value, the HCV RNA level will be considered undetectable or unquantifiable, respectively, at this visit for this subject. In addition, if a subject has an unquantifiable HCV RNA level at the preceding value and an undetectable HCV RNA level at the succeeding value, or vice versa, the HCV RNA level will be imputed as unquantifiable at this visit for this subject. For SVR analyses, if there is no value in the appropriate window after flanking imputation but there is an HCV RNA value after the window, then it will be imputed into the SVR window. Subsequent to this flanking and backward imputation, if a subject is missing a value for the visit window associated with the analysis, the subject will be imputed as a visit failure (i.e., not undetectable or unquantifiable).

If a subject starts another treatment for HCV, then all HCV RNA and PRO assessment values for this subject measured on or after the start date of the new HCV treatment will be excluded from analyses. The subject will be considered a failure for summaries of viral response at all time points after the start of the new HCV treatment.

HCV RNA < LLOQ Analyses for SVR

If a subject is missing an HCV RNA value for the visit window associated with the analysis of SVR after performing the imputations described above, then this value will be imputed with an HCV RNA value from a local laboratory if present; otherwise, the HCV RNA value for this visit will be missing. Subjects with missing HCV RNA data in the analysis window, after imputations, will be imputed as a failure.

HCV RNA Analyses for Relapse and Virologic Failure

If HCV RNA values from the central laboratory are missing but a local laboratory value is present in the appropriate time period, then the local laboratory value will be used to assess post-treatment relapse and on-treatment virologic failure.

Finally, missing sequence data will be imputed as follows in the analysis of the persistence of resistance from the sequences from PT Week 52 through PT Week 260 (5 years). If a signature variant is not detectable by population, clonal or deep sequencing at PT Week 24 (or later), the variant is imputed as not detectable at the PT Week 52 (or timepoints after the sequence with the variant not detectable) and time points thereafter if a sample from Post-Treatment Week 52 or later is not sequenced. If a signature variant is detectable by population, clonal, or deep sequencing at Post-Treatment Week 52 or later, then the variant is imputed as being detectable at earlier time points if the sample at the earlier time point is not sequenced.

7.0 Demographics, Baseline Characteristics, Medical History, and Previous/Concomitant Medications

Demographics, baseline characteristics, medical history, and previous/concomitant medications will be summarized overall and by presence of cirrhosis and genotype 1 subtype on the safety population.

